5.16.8. Laboratory Tests

The number and percent of patients with treatment-emergent abnormal, high, or low laboratory values for each laboratory test based on Covance reference ranges will be summarized.

Patients will be defined as having a treatment-emergent low value if they have all normal or high values at baseline, followed by a value below the lower reference limit at any postbaseline visit. Patients with all normal or high values at baseline (no low values) will be included in the analysis of treatment-emergent low laboratory values. Patients will be defined as having a treatment-emergent high value if they have all normal or low values at baseline, followed by a value above the upper reference limit at any postbaseline visit. Patients with all normal or low values at baseline (no high values) will be included in the analysis of treatment-emergent high laboratory values.

For analytes simply classified as normal or abnormal, patients will be defined as having a treatment-emergent abnormal value if they have all normal values at baseline, followed by an abnormal value at any postbaseline visit. Patients with all normal values at baseline will be included in the analysis of treatment-emergent abnormal laboratory values.

5.16.9. Immunogenicity

In the immunogenicity assay process, each sample is potentially examined multiple times, according to a hierarchical procedure, to produce a sample ADA assay result and potentially a sample NAb assay result. The cut points used, the drug tolerance of an assay, and the possible values of titers are operating characteristics of the assay.

It can be the case that the presence of high concentrations of galcanezumab will affect the measurements of the presence of ADA or NAb, and conversely high levels of ADA or NAb may affect the measurement of GMB concentration. Thus an GMB drug concentration, assessed from

a sample drawn at the same time as the ADA sample, plays a key role in clinical interpretation of a sample when the laboratory result is Not Detected.

5.16.9.1. Definitions of Patient ADA Status

Patient evaluable for TE ADA: A patient is evaluable for TE ADA if the patient has a non-missing baseline ADA result, and at least 1 non-missing postbaseline.

TE ADA positive (TE ADA+) patient: A patient who is evaluable for TE ADA is TE ADA+ if either of the following holds:

- **Treatment-induced:** The patient has baseline status of ADA Not Present and at least one postbaseline status of ADA Present with titer ≥ 20 (that is, 2^* MRD where for this ADA assay the MRD, the minimum required dilution of the ADA assay, is 10).
- **Treatment-boosted:** The patient has baseline and postbaseline status of ADA Present, with the postbaseline titer being 2 dilutions (4-fold) greater than the baseline titer. That is, the patient has baseline status of ADA Present, with titer 1:B, and at least one postbaseline status of ADA Present, with titer 1:P, with P/B ≥ 4 .

5.16.9.2. Immunogenicity Analyses to be Performed

To evaluate changes in immunogenicity data (ADA and NAb) after treatment, the number and percent of TE ADA evaluable patients who are TE ADA+ in Study CGAR will be tabulated.

The following analyses are planned:

- The incidence of TE ADA+ patients in CGAR postbaseline, by previous TE ADA status in the parent study (CGAL or CGAM) and at CGAR baseline. Because patients who enter Study CGAR will have differing levels of previous GMB exposure (0 to 15 months), this immunogenicity analysis will categorize patients in 3 groups, according to their previous GMB exposure in the parent study:
 - Study CGAL patients who received placebo (0 months of GMB treatment)
 - Study CGAL patients who received GMB (2 months of GMB treatment)
 - Study CGAM patients (12 or 15 months of GMB treatment)
- A listing of patients with TE ADA in CGAR postbaseline, including ADA and NAb results from both the parent study and CGAR.

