3.1. Study Rationale

Study CGAR is a Phase 3b study to assess the long-term safety and tolerability of galcanezumab 300 mg in patients with episodic or chronic cluster headache who have completed one of the Phase 3 double-blind, placebo-controlled studies, CGAL or CGAM.

Study CGAR will implement a dosing strategy to more closely approximate what may occur in clinical practice. For each patient, the study investigator will determine whether or not to dose galcanezumab 300 mg at each monthly interval based on clinical symptoms and response. Dosing will be no more frequent than once per month, and the investigator may choose to not dose galcanezumab for 1 or more months at their clinical discretion based on clinical efficacy. As such, some patients may receive monthly long-term treatment with galcanezumab for a period of months or years during the study, while others may have 1 or more months of galcanezumab dose-free intervals based on the investigator's judgment of clinical efficacy.

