5.1. Overall Design

Study CGAR is a Phase 3b single-arm, open-label safety study of galcanezumab 300 mg in outpatients with episodic or chronic cluster headache who completed Study CGAL or Study CGAM.

Please refer to the Protocol Operations Manual for information regarding the schedule of activities, study design, study tools, and patient scenario examples.

The study will consist of 2 SP:

- SP I is the screening phase to confirm patients meet the inclusion/exclusion criteria.
- SP II is the open-label treatment phase during which patients can receive galcanezumab 300 mg administered subcutaneously (SC) up to once a month.

Study Phase I: SP I is the screening phase. Patients will sign an informed consent document prior to completing any study-related screening procedures. SP I is the time from Visit (V)1 to V2. The minimum timeframe for SP1 needs to allow sufficient time for patients to washout of any excluded medications and to review subject eligibility. Visit 1 will be considered complete when the last procedure of the screening assessment for the patient is completed. Once Study CGAR is open for enrollment, potentially eligible patients may enter screening directly from the parent study, CGAL or CGAM. If a patient is not experiencing cluster headache attacks (e.g., in remission) they may wait to enter screening for CGAR until they anticipate experiencing or are experiencing a cluster headache attack. If patients had completed the parent study, CGAL or CGAM, prior to Study CGAR being open for enrollment, potentially eligible patients may still enter screening for Study CGAR. Study procedures for V1 (Event List A) of Study CGAR will be completed as follows:

- If the last visit of the parent study is also the first visit of Study CGAR, then electrocardiograms (ECGs), vitals, weight, hematology, clinical chemistry, urinalysis, hemoglobin A1C (HbA_{1C}), and serum pregnancy, C-SSRS, and Self-Harm Supplement Form/ Self-Harm Follow-up Form (SHSF/SHFU) from the last visit of the parent study will also be used for the first visit of Study CGAR.
- If the last visit of the parent study is ≤ 2 weeks from V1 of Study CGAR, the hematology, chemistry, HbA_{1C}, and urinalysis do not need to be repeated.
- If the last visit of the parent study is > 2 weeks from V1 of Study CGAR, all study procedures in Event List A need to be completed at the first visit of Study CGAR.

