6.1. Inclusion Criteria

1. Patients who **participated in and completed** either Study CGAL or Study CGAM. A study completer is defined as follows:
 - a. Study CGAL: a patient who has completed the double-blind treatment and post-treatment follow-up phases.
 - b. Study CGAM: a patient who has completed the double-blind treatment, open-label extension and post-treatment follow-up phases. However, if a patient entered Study CGAM prior to Study CGAR being open for enrollment, they will be considered a completer if they completed the double-blind treatment and post-treatment follow-up phases (e.g., opted not to participate in the open-label extension).
2. Investigator judges the patient as reliable to follow all study procedures, keep all study visits, and be compliant with study requirements.
3. Reproduction:
 - a. Women of child-bearing potential may participate in the study.
 - i. Women of child-bearing potential must test negative for pregnancy (based on a urine pregnancy test) at the time of enrollment and must agree to use either 1 highly effective method of contraception or a combination of 2 effective methods of contraception during the study. Women may choose to use a double barrier method of contraception. Barrier methods without concomitant use of a spermicide are not reliable or an acceptable method. Thus, each barrier method must include use of a spermicide. It should be noted that the

use of male and female condoms as a double barrier method is not considered acceptable due to the high failure rate when these methods are combined.

- b. Women not of child-bearing potential may participate in the study and include those who are:
 - i. Infertile due to surgical sterilization (at least 6 weeks after hysterectomy, bilateral oophorectomy or tubal ligation), congenital anomaly such as mullerian agenesis, or
 - ii. Post-menopausal, which is defined as:
 - a. A woman at least 50 years of age with an intact uterus, not on hormone therapy, who has had either
 - i. cessation of menses for at least 1 year, or
 - ii. at least 6 months of spontaneous amenorrhea with a follicle-stimulating hormone (FSH) level >40 mIU/mL; or
 - b. A woman 55 or older not on hormone therapy who has had at least 6 months of spontaneous amenorrhea; or
 - c. A woman at least 55 years of age with a diagnosis of menopause prior to starting hormone replacement therapy.
- c. Male patients agree to use at least 1 effective method of contraception during the study.

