Samples will be drawn at Month 0 (first dose), Month 1, Month 6, and then every 6 months, thereafter; prior to dosing unless dosing is temporarily halted due to a clinical efficacy response. When dosing is temporarily halted due to a clinical efficacy response, an immunogenicity sample is scheduled for 1 month after the last dose of galcanezumab. When dosing is resumed, an immunogenicity sample is drawn prior to dosing (Section 2, Schedule of Activities). Additionally, at study termination samples will be drawn approximately 1 month after the last dose of galcanezumab.

Samples will be retained for a maximum of 15 years after the last patient visit for the study, or for a shorter period if regulations and ERBs impose shorter time limits, at a facility selected by Lilly. The duration allows the sponsor to respond to future regulatory requests related to the investigational product.

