10.3.7. Immunogenicity Analyses

Refer to the SAP for details.

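### SAP 5.16.9.2 groups patients by prior galcanezumab exposure but labels every CGAM patient as 12 or 15 months, although criterion 1b admits CGAM patients who never entered the extension

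*SAP*

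**What the plan says.** SAP 5.16.9.2 notes that patients arrive in CGAR with between 0 and 15 months of earlier galcanezumab, and for that reason "this immunogenicity analysis will categorize patients in 3 groups, according to their previous GMB exposure in the parent study". The groups are CGAL placebo (0 months), CGAL galcanezumab (2 months), and a single row for everyone from the other parent study: "Study CGAM patients (12 or 15 months of GMB treatment").

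Protocol 6.1, criterion 1b, normally requires a CGAM patient to have finished the double-blind, open-label extension and follow-up phases. It makes an exception for anyone who entered CGAM before CGAR opened. That patient is "considered a completer if they completed the double-blind treatment and post-treatment follow-up phases (e.g., opted not to participate in the open-label extension"). Protocol 5.1 adds that patients who had finished the parent study "prior to Study CGAR being open for enrollment, potentially eligible patients may still enter screening for Study CGAR".

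Protocol 10.3.7 gives no immunogenicity analysis of its own ("Refer to the SAP for details"), so SAP 5.16.9.2 is the only place where the grouping is defined.

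**The concern.** The breakdown is meant to separate patients by how much galcanezumab they had before CGAR. For CGAL the rows follow the treatment received. For CGAM the row follows the study alone, and the months attached to it assume that every patient went through the extension. A CGAM patient admitted under the 1b exception is therefore put in the highest-exposure row, while the stated basis for grouping would put that patient near one of the two CGAL rows.

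If any such patient is TE ADA evaluable, the CGAM row mixes very different exposure histories under a label that describes only one of them. The incidence among CGAM patients as such would still be computed correctly. What fails is its reading as TE ADA incidence after 12 to 15 months of prior exposure, which is the reason for the split.

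**Working it through.** **Inputs**

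- Row labels in SAP 5.16.9.2: 0 months (CGAL placebo), 2 months (CGAL galcanezumab), 12 or 15 months (all CGAM).
- Two routes to being a CGAM completer in Protocol 6.1, criterion 1b: with the extension, or, for early entrants, without it.
- CGAM had a placebo arm. Protocol 3.1 describes the patients as having "completed one of the Phase 3 double-blind, placebo-controlled studies, CGAL or CGAM".
- The lengths of the CGAM phases are not given in either document.

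**Step 1: reproduce the CGAM label.** Let D be the months of double-blind treatment and E the months of extension.

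- Placebo, then extension: exposure = E.
- Galcanezumab, then extension: exposure = D + E.

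The two values must be 12 and 15, and D is positive, so E = 12 and D = 15 - 12 = 3. The label is thus exactly what extension completers would have. D = 3 is an inference from the label.

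**Step 2: exposure without the extension.**

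| CGAM double-blind arm | Prior exposure | Below the row's lower limit of 12 | Distance to nearest CGAL row |
|---|---|---|---|
| Placebo | 0 months | 12 - 0 = 12 months | 0 - 0 = 0 months |
| Galcanezumab | about 3 months (inferred) | 12 - 3 = about 9 months | 3 - 2 = about 1 month |

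The placebo line does not depend on D: no active treatment in the double-blind phase and no extension gives 0 months whatever the phase lengths.

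The example in criterion 1b is a patient who opted out of the extension, but the wording could also cover someone who began it and did not finish. Such a patient would fall between 0 and 12 months (placebo) or between 3 and 15 months (galcanezumab), so the gaps in the table are for those who skipped it altogether.

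**Step 3: does anything remove these patients from the row?**

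- SAP 5.16.9.1 sets evaluability without regard to parent-study path: "A patient is evaluable for TE ADA if the patient has a non-missing baseline ADA result, and at least 1 non-missing postbaseline".
- Protocol 9.4.5 sets one sampling schedule for all: "Samples will be drawn at Month 0 (first dose), Month 1, Month 6, and then every 6 months". A patient from any route can supply the baseline and a postbaseline result by Month 1.
- The planned listing links parent-study and CGAR antibody results, but only for patients with TE ADA, so it does not correct the row's denominator.

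Nothing excludes or reassigns them.

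**Step 4: size.** Let N be the TE ADA evaluable CGAM patients and k those among them without full extension exposure. The affected share of the row is k/N. With incidence p_full in the N - k others and p_low in the k, the row shows

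p_row = (1 - k/N) × p_full + (k/N) × p_low,

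so p_row - p_full = (k/N) × (p_low - p_full), which cannot exceed k/N in absolute size. Neither k nor N is in the documents. At k = 0 the difference is 0. Otherwise neither its size nor its direction can be determined.

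**The case against.** The strongest reply is that the label may simply be true. The exception covers only patients who entered CGAM before CGAR opened, and the documents show no one entering by it. The immunogenicity section was added in SAP Version 3, whose approval stamp is 02-Mar-2021, after interim cutoffs of 27 March 2018 and 04 September 2018 at which disposition and exposure were to be reported. In an open-label study the sponsor could have known which CGAM routes were represented. This stands as a plausible explanation, but the SAP does not say so. Its sentence on prior exposure is prospective, and a reader holding criterion 1b cannot tell whether the row is right.

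A second reply is that the harm is limited. The same analysis also splits incidence by TE ADA status in the parent study and at CGAR baseline, and TE ADA is judged against the patient's own CGAR baseline. Both limit how far a few low-exposure patients could mislead. Neither corrects the row's exposure label.

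A third reply is that the months are nominal descriptions of study paths and that every patient can be allocated without ambiguity. The allocation is indeed unambiguous. But the SAP names exposure, not study, as the basis for grouping, and 0 months is not a rounded form of 12.

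**Conclusion.** The concern holds as a minor point. As written, the grouping rule misplaces a protocol-eligible patient on its own criterion. For a CGAM placebo patient without the extension, this rests only on the documents. For a CGAM galcanezumab patient it also rests on the inferred 3-month double-blind phase.

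No effect on the results is shown, and none is claimed: it is nil if no such patient was enrolled and TE ADA evaluable. The issue is confined to one descriptive breakdown under the secondary immunogenicity objective. The overall TE ADA tabulation, the listing, each patient's TE ADA classification and the primary safety analyses are unaffected.

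**What to change.** Check whether any TE ADA evaluable CGAM patient lacked full extension exposure.

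- **If none:** say so in one sentence in the SAP or CSR and keep the present label.
- **If there are some:** derive the months (or doses) of galcanezumab actually received in the parent study and assign the exposure groups from that. Put the CGAM patients without full extension exposure in a row of their own or in the matching low-exposure group, and show parent study in the table.

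The cost in the second case is one derived variable and a short SAP edit. The planned listing already brings in parent-study antibody data, and no protocol text on this grouping has to change. The drawback is that some cells may be small, and a group that mixes CGAL and CGAM patients has to show parent study to be readable.

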5.17. Reports to Be Generated at Each Interim and Final Database Lock

5.17.1. Report to Be Generated at Interim Database Locks

Two interim locks will occur prior to the final database lock for CGAR, to support the regulatory submission and safety update report, respectively. The first lock will occur after all patients in both parent studies (CGAL and CGAM) have had the chance to complete the double-blind treatment phase, and the corresponding Synopsis CSR will include any data up to the cutoff date of 27 March 2018. The second lock for a safety update report will include any data up to the

cutoff date of 04 September 2018. The analyses for these two interim locks will focus on the following topics:

- patient disposition
- patient characteristics
- exposure to investigational products
- AE overview, TEAE, SAE, and DCAE

5.17.2. Report to Be Generated at Final Database Lock

For final database lock, all analyses defined in this SAP, including tables, figures, and listings, will be generated.

5.18. Clinical Trial Registry Analyses

Additional analyses will be performed for the purpose of fulfilling the Clinical Trial Registry (CTR) requirements. These analyses will be the responsibility of the Sponsor.

Analyses provided for the CTR requirements include the following:

A summary of AEs will be provided as a dataset that will be converted to an XML file. Both Serious Adverse Events and ‘Other’ Adverse Events are summarized: by MedDRA PT.

- An AE is considered “Serious” whether or not it is a TEAE.
- An AE is considered in the “Other” category if it is both a TEAE and is not serious. For each “Serious” AE and “Other” AE, for each term, the following are provided:
 - the number of participants at risk of an event
 - the number of participants who experienced each event term
 - the number of events experienced
- Consistent with www.ClinicalTrials.gov requirements, “Other” AEs that occur in fewer than 5% of patients in the treatment group may not be included if a 5% threshold is chosen.
- AE reporting is consistent with other document disclosures, for example, the CSR, manuscripts, and so forth.

6. Reference

- Brooks R. EuroQol: the current state of play. *Health Policy*. 1996;37(1):53-72.
- [EuroQol] EuroQol Group. EuroQol—a new facility for the measurement of health-related quality of life. *Health Policy*. 1990;16(3):199-208.
- Guy W. ECDEU assessment manual for psychopharmacology, revised 1976. Rockville, MD: National Institute of Mental Health, Psychopharmacology Research Branch. p 217-222. Available at: <https://archive.org/details/ecdeuassessmentm1933guyw>. Accessed September 29, 2014.

7. Appendices

Appendix 1. Important Protocol Deviations

Category (sCTMS)	Sub Category (sCTMS)	Trial-specific Term	Source
Informed Consent	Informed consent not obtained	NA	Programmable/Non-programmable–Monitor identified
Informed Consent	Revoke Consent	NA	Non-programmable–Monitor identified
Eligibility	Inclusion/Exclusion	Exclusionary cardiovascular-related condition	Programmable/Non-programmable–Monitor identified
Eligibility	Inclusion/Exclusion	Exclusionary hepatobiliary elevation	Programmable/Non-programmable–Monitor identified
Eligibility	Inclusion/Exclusion	Positive exclusionary UDS for any substances of abuse	Programmable/Non-programmable–Monitor identified
Eligibility	Inclusion/Exclusion	Inadvertent enrollment	Non-programmable–Monitor identified
Study Procedures	Excluded Con Meds	Use of verapamil at doses higher than allowed at baseline and during study	Programmable/Non-programmable–Monitor identified
Study Procedures	Other	C-SSRS not completed at required visits	Programmable/Non-programmable–Monitor identified
Study Procedures	Other	Missing all 3 BP, or all 3 Pulse	Programmable/Non-programmable–Monitor identified
Study Procedures	Other	Missing scheduled ECG	Programmable/Non-programmable–Monitor identified
Study Procedures	Other	Discontinuing without the 1 month post injection office visit (Event List F)	Programmable/Non-programmable–Monitor identified

Category (sCTMS)	Sub Category (sCTMS)	Trial-specific Term	Source
Safety	SAEs	Site did not appropriately report SAEs	Nonprogrammable – Monitor identified
Safety	Other	Female patients who are dosed who have a positive urine and/or serum pregnancy test	Programmable
Investigational Product	Patient took medication not fit for use	Patient received drug that was declared “Not Fit for Use”	Nonprogrammable – Monitor identified
Investigational Product	Other	Administering galcanezumab less than 21 days between doses	Programmable
Investigational Product	Dosing Error	Other Significant violations of study drug dosing	Nonprogrammable – Monitor identified
Investigational Product	Other	IP lost or stolen	Nonprogrammable – Monitor identified
Administrative/Oversight	Suspected Misconduct	NA	Nonprogrammable – Monitor identified
Administrative/Oversight	Suspected Misconduct	Suspected Fraud	Nonprogrammable – Monitor identified
Administrative/Oversight	Suspected Misconduct	Suspected falsification of data	Nonprogrammable – Monitor identified
Administrative/Oversight	Other	C-SSRS scale administered by unqualified rater	Nonprogrammable – Monitor identified
Administrative/Oversight	Other	Quality issue at site or vendor	Nonprogrammable – Monitor identified
Administrative Oversight	Other	Privacy Breach	Nonprogrammable – Monitor identified

Abbreviations: BP = blood pressure; C-SSRS = Columbia Suicide Severity Rating Scale; ECG = electrocardiogram; IP = investigational product; NA = Not Applicable; SAE = serious adverse event.

Leo Document ID = 45d3c3c2-da39-4860-9fa7-c1819cbcfb26

Approver: PPD

Approval Date & Time: 02-Mar-2021 18:12:37 GMT

Signature meaning: Approved
